11.3 ANALYSIS POPULATIONS

11.3.1 Efficacy populations

11.3.1.1 Modified intent-to-treat population

The primary population for analysis will be the modified ITT (mITT) population: ITT population with an evaluable primary endpoint. This will consist of all patients who receive at least 1 injection of investigational medicinal product, have a valid baseline % predicted FVC measurement, and have at least one post-baseline % predicted FVC measurement.

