11.4.2.2 Analyses of secondary efficacy endpoints

Disease progression, defined as decrease in absolute % predicted FVC $\geq 10\%$, or decrease in absolute % predicted DLCO $\geq 15\%$, or lung transplant, or death will be analyzed as a time to event variable. Patients not meeting the definition for disease progression will be considered censored at the time of their week 52 FVC assessment. For patients with a missing FVC assessment at week 52 the censoring time will be the time of the last measured FVC or DLCO assessment.

The time to disease progression will be compared between each active group and placebo using a log-rank test. The hazard ratio compared to placebo will be estimated from a Cox proportional hazards model.

The incidence of all-cause mortality will be calculated, but no hypothesis testing will be performed for this endpoint.

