**Table 1 - Protocol amendment statistical changes**

Amendment Number	Date Approved	Rationale	Description of statistical changes
10	21-Jul-2015	An early analysis of the main efficacy endpoints and safety data will be performed after the last patient completed the End of treatment visit (Visit 9, week 52) to allow an evaluation of the benefit/risk for the treatment of IPF with SAR156597 and take the decision to move to Phase 3 of clinical development and prepare for future phase 3 studies.	Not applicable.
10	21-Jul-2015	In case of major recruitment issues, a futility analysis could be considered in order to make further decisions regarding trial continuation/discontinuation.	No major recruitment issues occurred during the enrollment therefore no interim analysis was performed.
10	21-Jul-2015	Due to the recent approval of pirfenidone (Esbriet®) and nintedanib (Ofev®) and thus the availability on the market in almost all countries participating in the study, the rate of patients with authorized background therapy is likely to be higher than that initially expected at time of study design. In consequence, in order to limit the impact of background therapy on efficacy and safety assessment of SAR156597 for the treatment of IPF, the rate of patients in the background therapy stratum will be capped to a maximum of 66% (i.e., 33% in the without background therapy stratum).	In protocol: stratification factor was already planned for primary analysis but was not described for secondary analyses.  In SAP, description for secondary analyses and specification whether specific parameters will be described by With/Without Background Therapy status will be specified.
NA	NA	Duration of IMP exposure is defined as: last dose date – first dose date + 14 days, however for 200 mg SAR156597 q2w arm, there is an IMP injection every two weeks alternating with placebo the other week.	Duration of IMP exposure will be defined as: last dose date – first dose date + 7 days.
NA	NA	Change in mITT definition due a too low selection of patients (more than 5% of patients were discarded with the protocol definition).	The new definition is all randomized patients who take at least one dose or part of a dose of IMP. Patients will be analyzed using the treatment arm to which they were randomized. This results in considering all mITT patients

Amendment Number	Date Approved	Rationale	Description of statistical changes

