			in efficacy analysis provided that the endpoint was measured or could be calculated (e.g. at least 1 baseline and 1 post-baseline values for imputing and calculating a change).
NA	NA	Baseline definition has been revised because the timeslot between a screening and a baseline value is large (up to 4 weeks) and there will not be several assessments at 52 weeks.	Last available value before first IMP administration.
NA	NA	%predicted DLCO analysis is of interest, it was missing in protocol.	Addition of the %predicted DLCO exploratory endpoint analysis.
NA	NA	
Primary efficacy endpoint - change in week 52 missing data (due to death or lung-transplant) imputation approach: the time-to-death or lung transplant approach is more sensitive in ranking patients. For example, a patient who dies early will be more penalized than a patient who dies lately during the study.
 
Primary efficacy endpoint - change in week 52 missing data (due to reasons other death or lung-transplant) imputation approach:
 
 
patients taking treatment at 52 weeks will be imputed using a linear regression run on their treatment arm completers.
 
patients not taking treatment at 52 weeks will be imputed using a linear regression run on the placebo completers.
 
	
Time-to-death or lung transplants will be used instead of allocating the lowest rank for all died and lung transplanted patients.
 
For patients with a week 52 missing data (due to reasons other than death or lung transplant), depending on treatment intake at 52 weeks, a linear regression will be performed on a particular set of completers.

NA	NA	Disease progression endpoint - change in analysis cut-off date: Day 375 will be used instead of superior boundary of week 52 analysis window (Day 406) in order to prevent from non-random censures.	Patients not meeting the definition for disease progression will be considered censored at the time of their week 52 FVC or DLCO assessment provided that it was performed before Day 375. For patients with a missing week 52 assessment, the censoring time will be the time of the last measured FVC or DLCO assessment. For patients with week 52 assessment performed after Day 375, the censoring time will be Day 375.

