### **2.1.3 Efficacy endpoints**

Unless otherwise specified, all efficacy parameters values (scheduled or unscheduled) may be used to provide a value for the primary and secondary efficacy endpoints.

For FVC, FEV1 and FEV1/FVC parameters, a value is considered valid if this is an ATSBEST value with a grade “A” or “B” and a status “CLEAN” or “MANUAL”.

All measurements (scheduled or unscheduled) will be assigned to analysis windows defined in [Table 6](#), in order to provide an assessment of the efficacy parameter at each time point planned to be collected as per protocol. For all post-baseline time points, the value used for the analyses at a given time point (e.g at week 52) is the valid value obtained within the corresponding analysis window. If multiple valid values of a variable exist within an analysis window, the nearest from the targeted study day will be selected. In case of ties, the best value will be considered.

The baseline value is the last available and valid measurement obtained before or equal to the date and time of the first double-blind IMP injection. For patients randomized and not treated, the baseline value is defined as the last available and valid value obtained before or equal to the date and time of randomization.

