**Table 2 - Time-to-event variable definition for disease progression**

Scenarii	Event status	Event date
First event up to Day 375 is decrease in absolute % predicted FVC $\geq$ 10% or decrease in absolute % predicted DLCO $\geq$ 15%	event	Date of the 1 st decrease observed
First event up to Day 375 is death or lung transplant	event	Date of death or date of lung transplant
No event prior to last available and valid assessment of %predicted FVC or last available assessment of %predicted DLCO	censored	Min(date of last available %predicted FVC, date of last available %predicted DLCO)
No event up to Day 375 (last available and valid assessment of %predicted FVC and last available assessment of %predicted DLCO performed after Day 375)	censored	Date of Day 375

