##### *2.4.4.2.1 Disease progression endpoint*

The disease progression will be analyzed on the mITT population. Assessments at week 52 (performed before Day 375) will be used regardless of whether the patient has previously discontinued treatment. Only patients having a baseline and a post-baseline values in at least one time points analysis window for both the % predicted FVC and the % predicted DLCO parameters will be considered in the analysis. No week 52 missing data will be imputed for the disease progression.

The cumulative incidence of disease progression at 52 weeks will be presented graphically by treatment arm and background therapy status, using Kaplan-Meier method. The Kaplan Meier survival estimates (number of patients at risk, number of patients censored, number of disease progression events and probability of surviving without event (95% CI)) will be summarized by time points and overall (number of patients censored, number of events, median time to event).

The censoring reasons will be described by treatment arm and background therapy status.

The time to disease progression at 52 weeks will be tested comparing SAR156597 200 mg qw dose versus placebo using a log-rank test stratified on stratification factor (with/without Background Therapy) at a two-sided type I error level of 5%; and only if this comparison is significant will the SAR156597 200 mg q2w dose be tested versus placebo using a log-rank test stratified on stratification factor (with/without Background Therapy) at a two-sided type I error level of 5%.

The event rates for each of the 3 treatment arms, the hazard ratio and its 90 and 95% confidence interval (CI) compared to placebo for each active arm versus Placebo will be estimated from a

Cox model containing the treatment and the stratification factor variables. The underlying assumption of proportional hazards for Cox model will be checked by visual inspection.

In order to assess the significance, the magnitude and the repartition within components of the treatment effect of disease progression at 52 weeks, the following items will be described by treatment arm and by background therapy status:

- Summary of the disease progression at 52 weeks: number of events, event rates, p-values (only by treatment arm), estimated hazard ratios and their 90 and 95% CIs
- Description of each component as part of the disease progression: their number of events, event rates and their estimated hazard ratios

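### The disease-progression analysis admits only patients with baseline and post-baseline FVC and DLCO, so an early death or transplant is left out together with its event

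*SAP*

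**What the plan says.** SAP 2.4.4.2.1 places the disease-progression analysis on the mITT population and then narrows it: "Only patients having a baseline and a post-baseline values in at least one time points analysis window for both the % predicted FVC". The sentence goes on to require the same for % predicted DLCO. It contains no exception.

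SAP 2.1.3.2.2 and Table 2 define the endpoint as the time from randomization to the first of four events: an FVC decline, a DLCO decline, lung transplant or death. The scenario "First event up to Day 375 is death or lung transplant" is coded as an event at its own date, with no lung-function condition. Event-free patients who are not followed beyond Day 375 are censored at "Min(date of last available %predicted FVC, date of last available %predicted DLCO").

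Protocol 11.4.2.2 says that the composite ending "or lung transplant, or death will be analyzed as a time to event variable", and it imposes no two-test condition. The protocol mITT (11.3.1.1) does require that patients "have a valid baseline % predicted FVC measurement, and have at least one post-baseline % predicted FVC measurement". DLCO is not mentioned there.

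SAP Table 1 explains why the SAP widened the mITT: "Change in mITT definition due a too low selection of patients (more than 5% of patients were discarded with the protocol definition"). SAP 2.3.1.1 now asks only for randomization and any dose. Table 1 also says that mITT patients enter an efficacy analysis when the endpoint was observed or can be derived. The change it lists for disease progression concerns the Day 375 cut-off and censoring ("the censoring time will be the time of the last measured FVC or DLCO assessment"). It does not mention a two-test entry rule.

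**The concern.** A death or transplant is a complete endpoint event as soon as it happens. The entry rule makes its inclusion depend on whether the patient first returned for two breathing tests, and patients who die early are those least likely to have done so. The event is then lost from both the event count and the risk set.

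The rule also removes a patient with a qualifying fall on one test and no usable pair on the other. An example is a DLCO decline in a patient with no gradable spirometry, since for FVC "a value is considered valid if this is an ATSBEST value with a grade" of A or B and an accepted status.

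Entry therefore depends on post-randomization data related to the outcome. If early events or missing tests differ by arm, the log-rank test and Cox hazard ratio can move in either direction. The death component of this endpoint will also not reconcile with the all-cause mortality analysis (SAP 2.4.4.2.2), which has no such filter.

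**Working it through.** **The plan's own figures.** The documents give no expected number of progression events or early deaths. The only sample-size figure, 92 per arm for the primary endpoint (difference 5, SD 12, two-sided 5%, 80% power), reproduces: the t-test solution is 91.4, rounded up to 92, with 80.3% power. It does not bear on this point.

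**The rules side by side**

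| Patient | Table 2 | SAP 2.4.4.2.1 |
|---|---|---|
| Dies or is transplanted before both post-baseline tests | Event | Excluded |
| Qualifying decline on one test, no usable pair on the other | Event | Excluded |
| Dies after both tests | Event | Event |

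The first scheduled post-baseline test is at Week 12 (SAP 2.1.3.1), so the first row mainly concerns events before then.

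**Assumptions, none from the documents.** Annual mortality m is 5% to 10% at a constant hazard. FVC decline is 20% and DLCO decline 12.5% a year, independent, so lung-function progression is 1 − 0.80 × 0.875 = 30%. Declines are detected at Days 85, 169, 253 and 365.

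**Early deaths.** The share dying before Week 12 is 1 − (1 − m)^(12/52).
- m = 5%: 1.18 per 100, or 3.5 per 300.
- m = 10%: 2.40 per 100, or 7.2 per 300.

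These are upper bounds on early deaths lost, because an early-termination or unscheduled test keeps a patient in.

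**Lone declines.** If 2% of patients (6 of 300) lack a usable pair on one test, the declines lost are between 6 × 0.125 = 0.75 and 6 × 0.20 = 1.2, about one per 300.

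**Hazard ratio, 5% placebo and 10% active mortality, closed form.**
- All mITT: event probabilities are 1 − 0.70 × 0.95 = 0.335 and 1 − 0.70 × 0.90 = 0.370. HR ≈ ln(0.630)/ln(0.665) = 1.13.
- Filtered: (33.5 − 1.18)/(100 − 1.18) = 0.327 and (37.0 − 2.40)/(100 − 2.40) = 0.354. HR ≈ ln(0.646)/ln(0.673) = 1.10.

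**Large-sample Cox simulation** (400,000 per arm, cut-off Day 375, Monte Carlo SE about 0.004; differences of 0.01 between runs do not matter)

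| Mortality, placebo/active | HR, all mITT | HR, filtered |
|---|---|---|
| 5%/5% | 1.00 | 1.00 |
| 5%/7.5% | 1.07 | 1.05 |
| 5%/10% | 1.14 | 1.10 to 1.11 |
| 10%/5% | 0.87 to 0.88 | 0.90 to 0.91 |

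For 5%/10% there are 71.0 events per 200 patients against 67.4 after filtering. The loss of 3.6 equals 1.18 + 2.40. The SE of the log HR is about 2/√71.0 = 0.237, and the shift is 0.13 SE. It is 0.06 SE if half the early deaths had both tests.

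**Trial size** (20,000 simulated trials, 100 per arm, unstratified log-rank; Z filtered minus Z for all mITT)
- 5%/5%: mean 0.00, SD 0.20. The 5% verdict changes in 1.8% of trials; type I error is 5.1% in both sets.
- 5%/10%: mean −0.14, towards zero; 5th to 95th percentile −0.53 to 0.24. The verdict changes in 3.1% of trials.
- 10%/5%: mean +0.14, again towards zero. The verdict changes in 3.3% of trials.

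**The case against.** **The exclusion is largely inherited.** The protocol places efficacy analyses on its mITT, which already left out a death with no post-baseline FVC. This stands. A reader might infer that the SAP created the whole exclusion; it did not. It removed the FVC condition from its mITT, restored it for this endpoint and added DLCO. Table 1's general proviso does not justify the filter for deaths and transplants, because those events can be dated without any test.

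**The loss is limited.** The Week 12 window opens at Day 2 (SAP Table 6), and early-termination assessments include FVC and DLCO (protocol 10.1.8 and 10.3.4). This stands and is why the counts above are upper bounds.

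**The effect is slight and hard to reconcile with a formal test.** Testing requires both doses to succeed on the primary (SAP 2.4.4.3), where deaths take the worst ranks, so doubled mortality on active is an unlikely route to it. If active reduces mortality, the filter is conservative. Most of the 3% change in verdict is noise, since 1.8% occurs with no mortality difference. All of this stands and limits the weight of the point.

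**The more-than-5% figure.** A reader might infer that over 0.05 × 300 = 15 patients, many of them early deaths, would be lost. The SAP does not split that figure by condition, and it may include undosed patients or those without a valid baseline. It cannot be used to size the loss.

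**Exempting only deaths and transplants would be enough.** That would cure the main part but still discard declines on a single evaluable test, each of which Table 2 counts as an event.

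**Conclusion.** The inconsistency is explicit: the entry rule discards events that Table 2 defines, on a key secondary endpoint. It is minor. With balanced losses the average shift is zero. With mortality doubled in one arm it is about 0.13 SE of the log hazard ratio, and about 0.06 SE if half the early deaths had both tests. These sizes rest wholly on assumed mortality, progression and missingness; lung-function progression was fixed at 30% and the components were treated as independent.

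The documents do not support two stronger readings. One is that early deaths are hidden: they remain in the primary ranking (SAP 2.4.4.1), all-cause mortality (2.4.4.2.2) and the safety tables (2.4.5.2). The other is that the filter favours the drug: the direction depends on which arm loses more events, and that is unknown. Whether the earlier of the two last test dates is the right censoring time for patients with both tests is a separate question and is not decided here.

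**What to change.** Replace the both-tests sentence in SAP 2.4.4.2.1 as follows.

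1. Analyse all mITT patients. Count every death and lung transplant from randomization to Day 375, whatever lung-function data exist.
2. Count an FVC or DLCO decline whenever that test is evaluable, meaning it has a valid baseline and a post-baseline value.
3. For event-free patients, keep the Table 2 rule when both tests are evaluable. When only one is, censor at its last assessment, capped at Day 375. When neither is, censor at Day 1, including when the baseline is missing.
4. Report by arm the number of patients with one or no evaluable test.
5. Keep the planned both-tests set as a sensitivity analysis, and list the entry rule in SAP Table 1.

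The missing-baseline clause in item 3 is needed. If 4% of one arm had no usable baseline and were carried event-free to Week 52, then at equal 5% mortality that arm's event probability would be 0.96 × 0.335 + 0.04 × 0.05 = 0.324. The HR would be ln(0.676)/ln(0.665) = 0.96 with no true difference.

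The cost is one sentence, added Table 2 rows and minor reprogramming. No new data are needed, because deaths and transplants are on dedicated e-CRF pages. There are two side effects. A patient with one evaluable test can show a decline only on that test: with 0% against 4% such patients and equal true risk, the HR was 0.98, against 1.00 in the filtered set. Untested event-free patients contribute no risk time while untested deaths count: with 1% against 4%, the HR stayed at about 1.00. The by-arm counts and the sensitivity analysis would show whether either matters.

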### **1.3 DETERMINATION OF SAMPLE SIZE**

Approximately 300 patients will be randomized in this study, 100 per treatment arm. Based on the enrollment in prior studies of this population approximately half of the patients are expected to be older than 65.

The sample size calculations are based on the primary efficacy variable of % predicted FVC change from baseline to week 52, with the following assumptions:

- A common standard deviation of 12% is assumed based on the data from previous trials (26)
- A 5% mean difference between each dose and placebo in change from baseline in % predicted FVC
- A 2-sided 5% significance level with 80% power

Ninety two (92) patients per treatment arm will yield 80% power to detect a 5 percentage point difference between the treatment groups and placebo. Additional patients will be randomized in each regimen to allow for dropouts; therefore, approximately 100 patients will be randomized into each treatment arm, for a total sample size of approximately 300 patients for the study.

[figure not shown]
As a rank-based method will be used for analysis the actual power may differ from these calculations, however, calculations based on the ASCEND study (28), which used the same analysis method and endpoint confirm that the planned analysis should have at least 80% power. No adjustment is made for multiplicity since a hierarchical testing procedure is proposed.

Calculations were made using nQuery Advisor 7.0.

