#### **2.1.3.1 Primary efficacy endpoint(s)**

The pulmonary function test % predicted FVC is planned to be assessed at baseline, Week 12 (Visit 6), Week 24 (Visit 7), Week 36 (Visit 8), Week 52 (Visit 9/End of treatment) and Week 64 (Visit 10/End of study).

The primary efficacy endpoint of the study is the absolute change from baseline in % predicted FVC at 52 weeks in the mITT population.

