##### *2.1.3.2.2 Disease progression endpoint*

Disease progression is defined as time from randomization to the first occurrence of any of the following events:

- decrease in absolute % predicted FVC $\geq$ 10% (as in [Section 2.1.3.1](#))
- decrease in absolute % predicted DLCO $\geq$ 15% (as in [Section 2.4.4.2.3](#))
- lung transplant (recorded on the dedicated e-CRF page during the study)
- death (recorded on the dedicated e-CRF page during the study)

Disease progression will be analyzed as a time-to-event variable: event date – randomization date + 1 day where the event date is described in [Table 2](#).

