- Description of each component as individual (all events will be considered meaning that a patient could be represented several times per component): their number of events, event rates, their estimated hazard ratios and their 90 and 95% CIs

In addition, the maximal absolute decrease in % predicted FVC and the maximal absolute decrease in %predicted DLCO will be described by categories ( $\geq 0$  and  $< 5\%$ ,  $\geq 5\%$  and  $< 10\%$ ,  $\geq 10\%$  and  $< 15\%$ ,  $\geq 15\%$  and  $< 20\%$ ,  $\geq 20\%$ ) at 52 weeks. Decomposition of events and maximal events will be explored at 24 weeks as well.

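### The stand-alone component analysis of disease progression lets a patient count several times per component, but gives no repeat-event rule, risk set or variance for its hazard ratios

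*SAP*

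**What the plan says.** SAP 2.1.3.2.2 defines the composite as "time from randomization to the first occurrence of any of the following events", so each patient contributes at most one event to it. Table 2 follows the same logic and dates a decline at the first decrease observed.

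SAP 2.4.4.2.1 then describes the components twice. One bullet treats each component as part of the composite and asks for events, rates and hazard ratios. The next treats each component on its own and adds that "all events will be considered meaning that a patient could be represented several times per component". For this second version the outputs are "their number of events, event rates, their estimated hazard ratios and their 90 and 95% CIs".

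The model named earlier in the section for hazard ratios is a "Cox model containing the treatment and the stratification factor variables". No recurrent-event form, robust variance or frailty term is mentioned for the components.

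**The concern.** A fall from baseline of at least 10 points in % predicted FVC, or at least 15 in % predicted DLCO, is a state that can last. A patient who crosses the threshold at Week 12 and stays below it meets the criterion again at Weeks 24, 36 and 52. Death cannot recur. Under the stated rule, FVC and DLCO counts therefore mix two things: how many patients declined, and how long and how often they were tested afterwards.

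The SAP also attaches confidence intervals to these results. If repeats from one patient enter an ordinary Cox model as separate events, the model takes them as independent information and its standard error is too small. A reader of the component table could then see more precision for a treatment effect on FVC or DLCO decline than the data hold.

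**Working it through.** **1. Can the same decline be counted again?**

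- FVC is scheduled at "Week 12 (Visit 6), Week 24 (Visit 7), Week 36 (Visit 8), Week 52 (Visit 9/End of treatment" (SAP 2.1.3.1). The protocol flow chart (1.2) puts DLCO at the same visits. That is up to four counts per patient per component.
- Unscheduled values may be used (SAP 2.1.3 and 2.5.5). The analysis windows, which pick one value per time point, do not apply to disease progression (SAP 2.5.4).
- Patients who stop treatment are asked for an end-of-treatment assessment and then for the scheduled FVC and DLCO visits (Protocol 10.3.4), so they may be tested more often.
- Table 2 dates the first decrease for the composite. No rule defines a second event within a component.

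Nothing in the text prevents re-counting.

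**2. The plan's own figure.** The documents give no event rate or hazard ratio for disease progression or its components. The only figure to reproduce is the primary-endpoint sample size, which sets the arm size used below. With a difference of 5, SD 12, two-sided 5% and 80% power, the normal formula gives 2 × (1.960 + 0.842)² × 12² / 5² = 90.4, so 91. The noncentral t gives power 0.798 at 91 and 0.803 at 92. The stated 92 is reproduced, and about 100 per arm are randomized.

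**3. Simulation.** 100 patients per arm, four visits, true hazard ratio 1, 3000 runs per setting. Assumed: a proportion p with a decline by Week 52, and a probability q that the decline is seen again at each later visit. An ordinary Cox model is fitted to all events, with patients staying at risk after an event.

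| p | q | Events per patient with an event | True SD of log HR | Model SE | 95% CI covers | 90% CI covers |
|---|---|---|---|---|---|---|
| 0.1 | 0.5 | 1.76 | 0.523 | 0.357 | 83.8% | 75.7% |
| 0.1 | 1.0 | 2.53 | 0.525 | 0.298 | 75.5% | 66.4% |
| 0.2 | 0.8 | 2.26 | 0.323 | 0.215 | 81.2% | 72.9% |
| 0.3 | 0.8 | 2.29 | 0.258 | 0.173 | 81.6% | 73.5% |
| 0.4 | 0.5 | 1.83 | 0.201 | 0.167 | 90.3% | 83.0% |
| 0.4 | 1.0 | 2.66 | 0.204 | 0.138 | 82.3% | 74.3% |

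Over all settings with q of 0.5 or more, the model SE is too small by a factor of 1.2 to 1.8. The nominal 95% interval covers 76% to 90%, and the 90% interval 66% to 83%.

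**4. Hand check of the row p = 0.3, q = 0.8.** Suppose the chance of a first decline is equal at each visit: 1 − 0.7^(1/4) = 0.085. The relative weights of a first decline at visits 1 to 4 are then 1, 0.915, 0.837 and 0.765 (sum 3.517). The mean number of later visits is (3 × 1 + 2 × 0.915 + 0.837) / 3.517 = 1.61. Events per patient with an event are 1 + 0.8 × 1.61 = 2.29.

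With 0.3 × 200 = 60 such patients there are about 137 events, and the approximate model SE is √(4/137) = 0.171, against √(4/60) = 0.258 for first events only. Coverage is about P(|Z| < 1.96 × 0.173/0.258) = P(|Z| < 1.31) = 81%. All agree with the table.

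**5. Where there is no narrowing.** If declines are never seen again (q = 0), the 95% interval covers 97% to 99%.

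**6. Two remedies, same settings with q of 0.5 or more.** First event per patient and component: 95% coverage 94.9% to 96.2%. All events with a patient-level sandwich variance: 94.2% to 96.0%.

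**The case against.** The strongest reply is that the authors probably did not intend repeat counting. The two component bullets form a familiar pair: first event only, then each component regardless of what came before. On that view the parenthesis means that a patient may appear in several components. Table 2 gives only first-decrease dates, and death cannot occur several times, so the literal wording cannot hold for every component. For outcomes that do recur (exacerbations and hospitalizations, SAP 2.4.4.2.3.1 and 2.4.4.2.3.2), the SAP names a negative binomial model. Here it names a Cox model, which would fit one event per patient.

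This stands as evidence of intent, and it limits what can be claimed. A reader might infer that the SAP prescribes re-counting at every visit and that the reported intervals will be too narrow. The documents do not establish that: no sentence makes a persisting decline a new event, and none says that the hazard ratio uses all events. The counts could use all events while the hazard ratio uses the first.

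A reader might also infer that the breakdown of the key secondary endpoint is distorted. It is not. The preceding bullet already breaks the composite down on a first-event basis. Maximal FVC and DLCO decreases are also tabulated by category, which involves no repeat counting.

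The reply does not make the text right. The wording is per component, the intervals are requested in the same bullet, and a programmer who follows it literally gets inflated counts and, with the named model, invalid intervals.

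**Conclusion.** Wrong as written, with low impact. The SAP states a counting rule that suits neither a lasting decline nor the only model it names, and leaves the event definition, risk set and variance open. Under the literal reading, each patient with a decline contributes about 1.8 to 2.7 events. If the Cox model takes all of them, 95% intervals cover about 76% to 90%.

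Those figures rest on assumed decline proportions (10% to 40%) and persistence (0.5 to 1.0), because the documents give neither. They vanish if declines never persist or if the hazard ratio uses first events only.

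Only the descriptive stand-alone FVC and DLCO results are affected. The first-event breakdown, the composite log-rank test, the testing hierarchy (SAP 2.4.4.3), the primary endpoint and the sample size are not.

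**What to change.** Replace the parenthesis in the stand-alone component bullet of SAP 2.4.4.2.1 with: *each component analysed separately as time to its first occurrence per patient, whether or not another component occurred earlier; a patient counts at most once per component and may appear in several components.* Report patients with the event, the rate, and the hazard ratio with 90% and 95% intervals on that basis. This settles the event rule, risk set and variance together, and matches the first-event logic of the composite.

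If a repeat-event analysis is really wanted, the SAP must define a new event, state the risk set after an event and use a patient-level robust variance. Counts would still depend on how often patients are tested unless the new-event rule excludes a persisting decline.

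The recommended change costs one sentence and simplifies the programming. It needs no new data.
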